10.1 Definition of Populations for Analyses

Patients who are removed from the study during the first course because of progression are considered evaluable for efficacy only if progression can be documented per RECIST 1.1 criteria. Patients who come off

treatment for reasons other than progression (and prior to establishing response) are evaluable for toxicity only.

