10 STATISTICAL METHODOLOGY

This is a phase II activity trial. We will accrue a minimum of 10 patients and a maximum of 35 evaluable patients at a rate of 2 patients per month. We estimate 7 patients will be inevaluable and thus need to be replaced. Therefore our total number of patients will not exceed 42. The primary outcome for this trial is the objective response or stable disease rate (CR + PR + SD), which is evaluated within approximately 8 weeks of treatment. A confirmatory evaluation will be made no sooner than 4 weeks from this event (8 weeks, if SD). Once a response category is confirmed, evaluation for objective responses will be made every 12 weeks as outlined in Sections 6 and 7.1.3. Our target objective response or stable disease rate is 20%. We will monitor the objective response or stable disease rate as patients accrue and are evaluated following the example of Thall and Simon.[17] We will stop the trial if we have evidence that the target objective response or stable disease rate cannot be met.

We will stop the trial early if $P(\text{objective response or stable disease rate} \geq 20\% \mid \text{data from the trial}) < 0.10$. That is, given the outcomes from the patients who have already been evaluated, if we determine that there is less than a 10% chance that the objective response or stable disease rate is 20% or more, we will stop the trial. This decision rule gives the following stopping rule. We assume a uniform prior distribution for the rate of objective response or stable disease. Stop the trial if: $[\# \text{ of patients with objective response or stable disease} / \# \text{ of patients evaluated}] < 1/10, 2/17, 3/24, 4/31$.

The operating characteristics of this study design are shown in the following table.

Operating Characteristics of Monitoring Rule				
Rate of CR + PR + SD	Probability of Stopping Early	P ₂₅	P ₅₀	P ₇₅
0.05	0.956	10	10	17
0.10	0.725	10	17	35
0.15	0.436	17	35	35
0.20	0.220	35	35	35
0.25	0.097	35	35	35

We will estimate the rate OF CR + PR + SD with a 90% credible interval once the study is complete. If we complete the study with 11 patients with treatment success (CR or PR or SD) among 35 patients total (31%), then our 90% credible interval for the success rate would be 20.5 to 45.5%.

We will also estimate the overall survival and progression free survival for patients on study with the product-limit estimator of Kaplan and Meier (1958). [18]

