10.2 Efficacy Analyses

10.2.1 Definitions of Endpoints

Survival: The observed length of life from study entry (1st treatment) to death or, for living patients, date of last contact.

Time to tumor progression: The time from date of initial treatment

Progression-free survival: The observed time from study entry (1st treatment) to date of tumor progression, date of death, or, for patients alive without tumor progression, date of last follow-up.

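### Section 10.1, read literally, drops some early stoppers from overall survival and PFS, which conflicts with how Sections 2.2.1, 10 and 10.2.1 describe those endpoints; the population needs to be stated

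*Combined protocol and SAP*

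**What the plan says.** Section 10.1 has two rules. One concerns withdrawal for progression in the first course: such patients "are considered evaluable for efficacy only if progression can be documented per RECIST 1.1 criteria". The other says that anyone who stops "treatment for reasons other than progression (and prior to establishing response) are evaluable for toxicity only". Neither rule names the endpoint it applies to.

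OS and PFS come next, in Section 10.2.1, under the heading for efficacy analyses. Section 7.1.6 also lists survival among the other efficacy parameters. The OS definition is "The observed length of life from study entry (1st treatment) to death or, for living patients, date of last contact". PFS also starts at first treatment. It ends at progression or death, with last follow-up used for patients alive without progression.

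The only population named for these curves is in Section 10: "We will also estimate the overall survival and progression free survival for patients on study with the product-limit estimator". Being on study is not defined. Secondary objective 2.2.1 refers to the survival of the cohort as a whole. Section 10.3 has an explicit rule covering eligible treated patients, including those removed early, but for safety only.

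On numbers, Section 10 says "We estimate 7 patients will be inevaluable and thus need to be replaced", and it caps total enrolment at 42.

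**The concern.** The two parts of the plan give different answers for the same patient. Take a woman who dies in week 5 without documented progression. Under Section 10.2.1 her death is an OS event and a PFS event. Under Section 10.1 she left treatment for a reason other than progression before a response was established, so she counts for toxicity alone.

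If Section 10.1 governs, membership in the curves depends on what happens after the clock starts. The window is about 8 weeks to the first assessment. It reaches about 16 weeks for stable disease, which Section 6.3 requires to be confirmed at least 8 weeks later. The exits in that window include early death, removal for severe toxicity (Section 5.3) and the symptomatic deterioration described in Section 7.1.4.3. Patients leaving for these reasons plausibly do worse than the rest, and omitting them would make OS and PFS look too long. Survival is a stated secondary objective, so its population should not be left to whoever runs the analysis.

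**Working it through.** **The plan's own count.** Section 10 gives 35 evaluable patients at most and 7 inevaluable: 35 + 7 = 42, as stated. The share is 7/42 = 16.7%. The plan states no OS or PFS figure, so there is nothing further to reproduce.

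**How far 7 applies.** It is the estimate for all inevaluable patients. It may include first-course progression without RECIST documentation. Because registration precedes treatment (Section 5.1), it may also include patients who were never dosed. It is therefore a ceiling for treated patients who stop for other reasons before response. The calculations below use it as that ceiling.

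**Effect on the OS median.** Assume exponential survival, median *m* in the 35 kept, and hazard ratio *h* for the 7 omitted versus the kept. The documents give neither *m* nor *h*. The all-treated median *t* solves

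(35/42)·0.5^(t/m) + (7/42)·0.5^(h·t/m) = 0.5

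and the relative error from reporting the kept patients only is m/t − 1, which does not depend on *m*. For h = 2, put x = 0.5^(t/m). Multiplying by 6 gives x² + 5x − 3 = 0, so x = (−5 + √37)/2 = 0.5414, t/m = 0.885 and m/t = 1.130.

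| Assumed h | t/m | Kept median relative to all treated |
|---|---|---|
| 0.5 | 1.108 | 9.8% shorter |
| 1 | 1.000 | no change |
| 1.5 | 0.932 | 7.3% longer |
| 2 | 0.885 | 13.0% longer |
| 3 | 0.826 | 21.1% longer |
| 4 | 0.792 | 26.3% longer |

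For example, a kept median of 12 months corresponds to an all-treated median of 13.3 (h = 0.5), 12.0 (h = 1), 10.6 (h = 2) or 9.5 months (h = 4).

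**A second assumption.** Suppose *d* of the 7 die early, before the median, and the others do as well as the kept patients. Then ((42 − d)/42)·0.5^(t/m) = 0.5. For d = 1, 3 or 7, t/m = 0.965, 0.893 or 0.737, and the kept median is 3.6%, 12.0% or 35.7% too long.

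**PFS.** If the omitted patients were followed to an event, the table applies unchanged. Section 6.5 leaves imaging after treatment to the physician, so many might be censored soon after stopping. Assume a kept PFS median of 3 months and censoring of the 7 spread evenly between 0.25 and 2 months. The all-treated median is then about 3.1 (h = 0.5), 3.0 (h = 1), 2.83 (h = 2) or 2.61 months (h = 4). At h = 2 the kept median is 3.00/2.83 − 1 = 6% too long, and at h = 4 it is 3.00/2.61 − 1 = 15% too long. These are about half the uncensored figures.

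**The case against.** The best reply is that the plan already means to include everyone treated. Section 10 gives the Kaplan-Meier estimates their own population, worded differently from the evaluable patients used for monitoring. Section 10.2.1 starts at first treatment and counts every death. Objective 2.2.1 speaks of the cohort. Section 7.1.1 uses evaluability for toxicity and for response, and the parenthesis about establishing response in Section 10.1 fits that split. Section 4.4 asks that outcome be documented where possible, and Section 6.5 requires follow-up data every 6 months. On this view the only link from Section 10.1 to OS and PFS is a heading.

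Much of this stands. A reader might infer that the plan definitely excludes these patients, because other sections call those who stop off study. That argument proves too much: Section 6.3 uses the same phrase for patients with progressive disease, and PFS cannot have been meant to lose its progressors. The evidence of intent favours inclusion. But the restriction in Section 10.1 has no exemption, the plan labels survival as efficacy, and the explicit rule for treated patients was written only for safety. The intent still has to be guessed.

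A reader might also infer that both curves are bound to look longer. The documents do not support that. They say nothing about the omitted patients' prognosis, and refusal, non-compliance, physician's choice and loss to follow-up have no fixed direction.

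Finally, OS and PFS are descriptive single-arm estimates, and no stopping rule or decision uses them. That is correct and limits the weight of the point.

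**Conclusion.** The conflict is real and unresolved: the population for OS and PFS cannot be settled from the text. Literal use of Section 10.1 would select on post-baseline events and could remove up to 7 of 42 patients (17%), a ceiling rather than an expected number.

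Upward bias is plausible but conditional on the omitted patients doing worse. With exponential survival and all 7 omitted, the OS median would be about 10% too short at a hazard ratio of 0.5, correct at 1, 13% too long at 2 and 26% too long at 4. The PFS effect is smaller if early stoppers would be censored early. The hazard ratios, medians and censoring pattern are assumptions. The primary CR+PR+SD rate and its stopping rule are outside this point.

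**What to change.** 1. In Section 10.1, limit both sentences to the CR+PR+SD endpoint. Changing only the toxicity sentence would leave the first-course progression rule removing patients from OS and PFS on the same literal reading.
2. In Section 10, replace the undefined on-study population with a statement that the Kaplan-Meier estimates of OS and PFS include all patients who received at least one dose of study drug, whether or not they are evaluable for response or were replaced. Where the outcome is unknown, censor at last contact (OS) or last follow-up (PFS).

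The cost is wording only. No new data collection is needed beyond the follow-up that Sections 4.4 and 6.5 already request, and patients with incomplete follow-up are censored. The reported medians may be slightly shorter.

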6.1 Schedule of Assessments

Assessments	Screening / baseline	Weekly	Every cycle	Every 2 nd / 3 rd cycle ^d	End of treatment ^j	Follow-up ^h
Medical history	X ^a					
Physical examination	X ^{b,c}		X ^c		X	X
Vital signs	X ^b		X		X	X
Zubrod Performance Status	X ^b		X ^b		X	X
Weight	X ^b		X		X	X
CBC with differential and platelets	X ^b		X		X	
Hepatitis screening/monitoring	X ^{l,n}		X ^{m,o}			
Serum chemistries (Mg+, SGPT, total bilirubin, BUN, serum creatinine/creatinine clearance) and electrolytes, glucose	X ^{b,p}		X		X	
Lipid panel (Triglycerides, LDL, HDL)	X ^b		X		X	
Tumor staging (baseline tumor measurements)	X ^{a,e}					
Chest x-ray	X ^a			X ⁱ	X ⁱ	
CT/MRI of chest, abdomen and pelvis and/or appropriate imaging	X ^{a,e}			X ^f	X ^f	X
Toxicity	X ^a	X ^g	X		X	X
Tumor response				X		
Serum estradiol ^k	X ^a					
Medication compliance/pill count			X ^q			

- a Within 4 weeks prior to Step 2 of study registration (treatment assignment)
- b Within 7 days of initiation of therapy
- c Pelvic exam every cycle if disease is in the pelvis. Otherwise, pelvic exam is done at baseline, after 2 cycles, and then every 3rd cycle thereafter.
- d Obtained after the first two cycles (approximately 8 weeks), after four cycles (approximately 16 weeks) for confirmation, then every three cycles (approximately 12 weeks) thereafter.
- e CT/MRI of chest only in patients with chest disease.
- f Using the same imaging technique used during the initial evaluation.
- g Toxicity will be assessed on an ongoing basis.
- h Follow-up time interval at the physician's discretion. Follow up begins after the patient stops study medication.
- i Only in patients with chest disease
- j Within 4 weeks of the last dose of study drug.
- k Documentation of a serum estradiol < 10 pg/mL is required only for patients in whom hysterectomy was performed premenopausally and in whom bilateral oophorectomy was not completed. Estradiol is not required for women known to be menopausal or surgically castrated.
- l Hepatitis B Virus testing: Prior to randomization (or starting study drug in non-randomized trials), the categories of patients listed in Section 3.2 should be tested for hepatitis B serologic markers and viral load: HBV-DNA HBsAg, HBc Ab, and HBs Ab.
- m HBV DNA monitoring should be done depending on results from serologic markers and viral load as listed in Table 3-3.

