After this first evaluation, patients with progressive disease will be taken off study. To be assigned a status of PR or CR according to RECIST 1.1, tumor measurements must be confirmed by repeat studies (i.e., evaluation of measurable tumor, physical exam, and imaging) that should be performed no less than 4 weeks after the criteria for disease control are first met. To be assigned a status SD, tumor measurements must be confirmed by repeat studies (i.e., evaluation of measurable tumor, physical exam, and imaging) that should be performed no less than 8 weeks after the criteria for disease control are first met.

After these confirmatory studies, to be obtained every 3 cycles (12 weeks):

1. Pelvic exam
2. CT/MRI scan and/or appropriate imaging (the same imaging technique used during the initial evaluation will be performed)
3. Chest imaging (only in patients with chest disease)

6.4 End of Treatment: To be obtained at the end of treatment:

1. Physical exam including pelvic exam
2. Vital signs
3. Zubrod performance status
4. Weight
5. Complete blood count with differential and platelets, serum chemistries (magnesium, SGPT, total bilirubin, BUN, serum creatinine, glucose and electrolytes).
6. Lipid panel (Triglycerides, LDL, HDL)

7. CT/MRI scan of chest, abdomen and pelvis and/or appropriate imaging (the same imaging technique used during the initial evaluation will be performed). Chest imaging (only in patients with chest disease)
8. Assessment of treatment related toxicities
9. Medication compliance/pill count and return of unused medication

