7.1.1 Definitions

Evaluable for toxicity. All patients will be evaluable for toxicity from the time of their first treatment with Letrozole (Evirolimus) and RAD001.

Evaluable for objective response. Only those patients who have measurable disease present at baseline, have received at least one cycle of therapy, and have had their disease re-evaluated will be considered evaluable for response. These patients will have their response classified according to the definitions stated below. (Note: Patients who exhibit objective disease progression prior to the end of cycle 1 will also be considered evaluable.)

Evaluable Non-Target Disease Response. Patients who have lesions present at baseline that are evaluable but do not meet the definitions of measurable disease, have received at least one cycle of therapy, and have had their disease re-evaluated will be considered evaluable for non-target disease. The response assessment is based on the presence, absence, or unequivocal progression of the lesions.

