7.1.4.3 Evaluation of Best Overall Response

The best overall response is the best response recorded from the start of the treatment until disease progression/recurrence (taking as reference for progressive disease the smallest measurements recorded since the treatment started). The patient's best response assignment will depend on the achievement of both measurement and confirmation criteria.

For Patients with Measurable Disease (i.e., Target Disease)

Target Lesions	Non-Target Lesions	New Lesions	Overall Response	Best Overall Response when Confirmation is Required*
CR	CR	No	CR	≥4 wks. Confirmation**
CR	Non-CR/Non-PD	No	PR	≥4 wks. Confirmation**
CR	Not evaluated	No	PR	
PR	Non-CR/Non-PD/not evaluated	No	PR	
SD	Non-CR/Non-PD/not evaluated	No	SD	documented at least once ≥4 wks. from baseline**
PD	Any	Yes or No	PD	no prior SD, PR or CR
Any	PD***	Yes or No	PD	
Any	Any	Yes	PD	

* See RECIST 1.1 manuscript for further details on what is evidence of a new lesion.

** Only for non-randomized trials with response as primary endpoint.

*** In exceptional circumstances, unequivocal progression in non-target lesions may be accepted as disease progression.

Note: Patients with a global deterioration of health status requiring discontinuation of treatment without objective evidence of disease progression at that time should be reported as “*symptomatic deterioration*.” Every effort should be made to document the objective progression even after discontinuation of treatment.

For Patients with Non-Measurable Disease (i.e., Non-Target Disease)

Non-Target Lesions	New Lesions	Overall Response
CR	No	CR
Non-CR/non-PD	No	Non-CR/non-PD*
Not all evaluated	No	not evaluated
Unequivocal PD	Yes or No	PD
Any	Yes	PD

* ‘Non-CR/non-PD’ is preferred over ‘stable disease’ for non-target disease since SD is increasingly used as an endpoint for assessment of efficacy in some trials so to assign this category when no lesions can be measured is not advised

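### Section 10.1, read literally, drops and replaces a patient who stops for a non-progression reason even when her end-of-treatment scan documents progression; section 7.1.1 counts her

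*Combined protocol and SAP*

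**What the plan says.** Two sections define who enters the efficacy denominator.

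- **Section 10.1** goes by the reason for stopping. Patients removed for progression during the first course "are considered evaluable for efficacy only if progression can be documented per RECIST 1.1 criteria". A different rule covers everyone who stops early for another cause: those who leave "treatment for reasons other than progression (and prior to establishing response) are evaluable for toxicity only". It makes no exception for a scan done after the decision to stop, and it does not define when a response is established.
- **Section 7.1.1** goes by what was observed. Patients with measurable disease at baseline who "have received at least one cycle of therapy, and have had their disease re-evaluated will be considered evaluable for response". A note adds: "Patients who exhibit objective disease progression prior to the end of cycle 1 will also be considered evaluable". The reason for stopping plays no part.

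Section 10 caps evaluable patients at 35, expects 7 to be inevaluable and replaced, and limits the total to 42. Replacement comes from there, not from 10.1.

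The protocol also plans to collect the outcome in question. Section 6.4 lists "CT/MRI scan of chest, abdomen and pelvis and/or appropriate imaging" at the end of treatment, and footnote j of the schedule in 6.1 times that visit: "Within 4 weeks of the last dose of study drug". For patients who stop because of deteriorating health without objective progression, 7.1.4.3 adds: "Every effort should be made to document the objective progression even after discontinuation of treatment".

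**The concern.** Take a patient with measurable disease who completes one cycle, stops for toxicity in week 6, and shows RECIST 1.1 progression on the scheduled end-of-treatment scan. Under 7.1.1 she is evaluable and a failure. Under the literal wording of 10.1 she contributes to toxicity only, and section 10 then replaces her.

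The case is plausible. Section 5.3 removes patients for recurrent grade 3 non-hematological toxicity, for most grade 4 toxicity and for long interruptions. In the earlier single-agent everolimus trial described in section 1.5, 17 of 35 patients needed a dose reduction.

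At stake are the denominator of the primary CR + PR + SD rate and the count of patients evaluated in the futility rule. For a documented progressor the bias has one direction: a known failure is exchanged for a patient who may succeed. If the conflict is left open, it may be settled after outcomes are known.

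**Working it through.** **Inputs, all from section 10.** At most 35 evaluable patients, 7 replaced, 42 in total. Uniform prior. Stop if P(rate ≥ 20% | data) < 0.10, which the protocol gives as fewer than 1/10, 2/17, 3/24 or 4/31 successes. Worked example 11/35 with a 90% credible interval of 20.5 to 45.5%.

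**Step 1: reproduce the plan's figures.** The posterior after x successes in n patients is Beta(1 + x, 1 + n − x).

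- Boundaries: P(rate ≥ 20%) is 0.086 at 0/10, 0.099 at 1/17, 0.098 at 2/24 and 0.093 at 3/31. All are below 0.10.
- 11/35: the 5th and 95th percentiles of Beta(12, 25) are 20.5% and 45.5%, an exact match.
- Probability of early stopping, by exact binomial recursion over the four looks:

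| True rate | Protocol | Recomputed |
|---|---|---|
| 0.05 | 0.956 | 0.955 |
| 0.10 | 0.725 | 0.723 |
| 0.15 | 0.436 | 0.432 |
| 0.20 | 0.220 | 0.220 |
| 0.25 | 0.097 | 0.101 |

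The design arithmetic is sound. The problem lies in who is counted.

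**Step 2: one swapped patient in the 11/35 example.** Because evaluable patients are capped at 35, a retained progressor takes the place of her replacement.

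- If the replacement would have failed, the result stays 11/35 = 31.4% (20.5 to 45.5%).
- If the replacement would have succeeded, retaining the progressor gives 10/35 = 28.6%, with Beta(11, 26) limits of 18.2 to 42.5%.
- Assume the replacement succeeds with probability 11/35. The expected change is (11/35) × (1/35) = 0.0090, or about 0.9 percentage points.

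**Step 3: effect on the futility rule.** Let q be the share of otherwise countable patients who are dropped as documented progressors. All of them are failures, so a true rate p is monitored as p/(1 − q). The documents do not give q; the values below are assumptions.

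| Assumed q | p = 0.10 monitored as | P(stop) | p = 0.20 monitored as | P(stop) |
|---|---|---|---|---|
| 0 | 0.100 | 0.723 | 0.200 | 0.220 |
| 1/36 | 0.103 | 0.706 | 0.206 | 0.202 |
| 2/42 | 0.105 | 0.693 | 0.210 | 0.190 |
| 7/42 | 0.120 | 0.603 | 0.240 | 0.119 |

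The last row supposes that all 7 planned replacements are such progressors. It is an outer limit, not an expectation. The boundaries depend only on the prior, the 20% target and the 0.10 cut-off, so they do not move.

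**The case against.** **A milder reading exists.** Section 10.1 itself makes documented first-course progression count for efficacy, 7.1.1 does the same, and section 10 speaks of confirming a response category. Read together, toxicity-only status could be meant just for patients with no usable tumor assessment. This is a fair reading, and it rules out saying that the plan certainly discards these failures. It does not close the question. Section 10.1 names progression separately from response, and section 3 defines response rate as SD, PR or CR. Even if progression is a response category, a patient whose scan follows her last dose left treatment before that category was established.

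**The group is narrow and uncounted.** The patient must stop for another reason before response is established and then show RECIST progression on a scan within 4 weeks of the last dose. This stands, and it keeps the point small.

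**A reader might infer more than the documents support:**

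- *That the 7 planned replacements are hidden failures.* Section 10 does not say why they would be inevaluable.
- *That the final conclusion could flip, because the lower limit falls from 20.5% to 18.2% at 10/35.* Section 10 uses the interval for estimation only and attaches no success rule to it.
- *That 10.1 must also make an unconfirmed SD, PR or CR before a toxicity stop a failure.* Section 6.3 requires SD to be confirmed "no less than 8 weeks after the criteria for disease control are first met", but the table in 7.1.4.3 asks only for SD documented once at 4 weeks or more from baseline. The texts pull apart, and the choice matters: if 7 in 42 would-be successes became failures (again an assumption), a true 20% would be monitored as 0.20 × 35/42 = 16.7%, and P(stop) would rise from 0.220 to 0.350. That is a separate endpoint decision.

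**Conclusion.** The conflict is real and should be resolved. Sections 7.1.1 and 10.1 classify the same patient differently, nothing says which prevails, and the literal form of 10.1 favours the treatment. The effect is small: about 0.9 points expected per swapped patient at 11/35, and at an assumed 1 in 36 a fall of 0.017 to 0.018 in the probability of stopping early at true rates of 10% and 20%.

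These figures rest on the literal reading of 10.1, on a replacement who succeeds at the observed rate, and on assumed values of q. They show direction and scale; they are not a forecast. The protocol's boundaries, stopping probabilities and credible interval need no correction.

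**What to change.** Add one sentence to section 10.1:

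*A patient with measurable disease and RECIST 1.1 progression documented on or before the scheduled end-of-treatment assessment (within 4 weeks of last dose) is evaluable for efficacy and counts as a failure, whatever the reason for stopping; she is not replaced.*

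The time limit is deliberate. Follow-up imaging under section 6.5 is at the physician's discretion. Without a limit, a patient who stopped early could enter the denominator later only if a discretionary scan happened to show progression.

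The cost is a one-sentence amendment and a slightly less favourable rate. No test is added, because the scan is already scheduled.

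The handling of SD, PR or CR seen once but not confirmed before a toxicity stop (6.3 against the 7.1.4.3 table) is for the sponsor to decide separately. This sentence leaves it open.
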